3.4 SOCIOECONOMIC FACTORS

We are studying how race, socioeconomic status (SES), and medical care use and access are associated with sarcoidosis disease status at presentation and disease progression over time. Specifically, we will test the hypotheses that: sarcoidosis patients will be more likely to be of low SES than controls; sarcoidosis patients with low SES will present with more severe disease and have greater disease progression in two years than patients with high SES; sarcoidosis patients with low SES will have less access to medical services than sarcoidosis patients with high SES; and sarcoidosis patients with low SES will comply less with medical treatment (including adherence to medication), return less regularly for follow-up visits and maintain less continuity of care than patients with high SES. Similar relationships are expected in all racial groups.

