6.2 CASE SELECTION

It is planned that the total study population will consist of 720 cases and 720 controls. Each Clinical Center enrolls, interviews, examines and collects blood specimens from 72 cases with sarcoidosis and enrolls, interviews and collects blood specimens from 72 matched controls during the recruitment period (November 1, 1996 through June 30, 1999).

Cases may be recruited from a variety of clinical settings, including inpatient, hospital-based outpatient, and non hospital-based outpatient. Each Principal Investigator defines, in advance, the geographic area from which the center recruits patients for the study. Permission to contact patients identified in a clinical setting must be obtained initially from the attending physician of record, in advance of study enrollment. Potential cases are informed that a payment will be given to reimburse them for parking costs, meals and other expenses (including lost time from work) at the medical center, and transportation costs.

At the time of enrollment into the study, patients are categorized according to their clinical condition at the time of initial diagnosis, i.e., the day of biopsy confirmation. Table 6-2A outlines the disease categories that were used to describe cases beginning November 1996. An additional revised classification system was used beginning September 1997 and is given in Table 6-2B. The purpose of revising the disease categories is to encourage use of information on facets of the clinical presentation of sarcoidosis that were not readily appreciated in the hierarchical, initial classification of disease categories. This information is used in ACCESS to assess the spectrum of clinical sarcoidosis presentations represented among the ACCESS cases.

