6.3 CONTROL SELECTION

There is one population-based control group, selected for the study through random digit dialing. Controls are matched to cases on age (within five years), gender and self-designated race (black, white, other).

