6.3.1 Random Digit Dialing Controls

Cases are matched in a one to one ratio to controls selected through random digit dialing. Random digit dialing facilitates the selection of a control group that approximates a probability sample in the population. Random digit dialing (RDD) is used to identify potential controls through an unbiased clustered random sample of households with telephones (Waksberg, 1978). Cluster sampling of telephone households and a stratified sample of age-, gender-, and self-identified racematched individuals are used (Hartge et al, 1984).

The groups selected to generate telephone numbers, Survey Sampling Inc. (SSI), and to perform the telephone recruitment of potential controls, Telesurveys Research Associates (Random Digit Dialing (RDD) Interview Group), work under the direction of the Clinical Coordinating Center. The RDD callers are responsible for making initial telephone contact with potential controls in the geographic areas of the Clinical Centers.

Once the RDD Interview Group recruiter has established the eligibility, availability and willingness of the potential control to participate, the potential control is informed that an interviewer from the Clinical Center will be in touch soon to set up an appointment to meet for questionnaire

administration and phlebotomy. Potential controls are informed that a payment will be given to them after they complete the study interview to reimburse them for parking costs, meals and other expenses (including lost time from work) at the medical center, and transportation costs.

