6.4 INCLUSION/EXCLUSION CRITERIA AND CONFIRMATION OF ELIGIBILITY

Only patients 18 years of age or older may be enrolled in the study. Patients cannot have active tuberculosis or be taking anti-tuberculosis therapy. Potential controls with a past history of sarcoidosis, chronic beryllium disease, fungal diseases treated with systemic chemotherapy, granulomatous hepatitis, primary biliary cirrhosis, Bell's palsy, uveitis, Crohn's disease, and erythema nodosum of unknown etiology are excluded from the study.

Potential cases and controls must be competent to sign consent forms for study participation and must be willing to participate for the length of the study. They may be excluded from the study if there is evidence that they may not comply with all study requirements. Potential cases and controls must be able to respond directly to questions on the study forms to be eligible for inclusion in the study. The eligibility of potential cases and controls is determined by the Clinical Center Coordinator through a combination of record review and telephone and personal interview. The Coordinator explains the nature of ACCESS to the potential cases and controls. If the potential case or control is interested in participating in ACCESS, the Coordinator administers a brief structured questionnaire addressing eligibility issues not gleaned from the medical record or telephone interview.

Potential cases and controls who are eligible and agree to enrollment, are asked to sign one or more consent forms to participate, depending upon the individual's case/control status (see Chapter 7). Cases and controls are identified only by a patient name code and identification number. The patient's name code and identification number serve to conceal the personal identity from the ACCESS Clinical Coordinating Center and Clinical Center staff and to maintain confidentiality. The patient's name code and identification number are recorded on separate ACCESS logs for cases and controls. These logs include the following information:

- 1. Date of initial contact.
- 2. Age.
- 3. Gender.
- 4. Race.
- 5. Health care coverage.

The reasons for ineligibility are recorded for all cases and controls deemed ineligible to participate in ACCESS. As noted in Section 6.2 completion of screening logs for cases was discontinued in October 1997.

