7.2 ORIENTATION OF CONTROLS

Controls are informed of the nature of the study and the method by which they were invited to participate. Potential controls are informed that random digit dialing methods are used to identify individuals with age, gender, and race matching those of a particular patient with sarcoidosis within the same telephone exchange.

Controls are informed that their participation in the study involves an interview with completion of a questionnaire and collection of a blood sample. There are no other procedures, and no follow-up is planned. Controls are informed that they will be reimbursed for their expenses to participate in the study. The amount varies among Clinical Centers and depends upon whether or not the individual has to make a special trip to the Clinical Center. Each individual receives a minimum of \$25 for ACCESS-related expenses.

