12.3.2.2 Matched Case Control Designs

Cases and controls will be matched with respect to the case's age (± five years), gender, and race. Random digit dialing may implicitly match cases and controls for geographical location. A matched design will be most appropriate for analyzing the data in this study. Simple presentations of matched case control data should follow the methods outlined by Breslow and Day. Categorical data will be presented using a cross tabulation of the number of cases exposed versus the number of controls exposed. Standard chi-square analyses will not be performed on these tables. Instead, methods for estimating the odds ratio from McNemar's test will be used to estimate the measure of association. Since the proposed number of cases is large, it will be possible to estimate 95% confidence intervals using the binomial approximation. For continuous variables, presentation of means will be accomplished using a paired t-test. These analyses can be performed using Proc Means in SAS. This will have the effect of adjusting for the matching variables. A point estimate for the difference in case and control means will be obtained and a 95% confidence interval for the difference will be calculated using this procedure.

It will be important to adjust study results for confounding variables that could bias the results of the case control study. Analyses using one more exposure variable(s) will be performed using conditional logistic regression methods. This method can be used to estimate odds ratios for casecontrol studies.

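### Controls can come only from telephone households but cases need no telephone, so the case-control test of low SES in section 3.4 compares unlike source populations

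*Protocol*

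**What the plan says.** **Controls.** Section 6.3.1 says random digit dialing is used to "identify potential controls through an unbiased clustered random sample of households with telephones". The same section claims that "Random digit dialing facilitates the selection of a control group that approximates a probability sample in the population". Section 6.3 fixes the matching: "Controls are matched to cases on age (within five years), gender and self-designated race (black, white, other". Neither SES nor telephone ownership is a matching variable.

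**Cases.** Section 6.2 states: "Cases may be recruited from a variety of clinical settings, including inpatient, hospital-based outpatient, and non hospital-based outpatient". The case definition (6.1), case selection (6.2) and eligibility rules (6.4, which opens with "Only patients 18 years of age or older may be enrolled in the study") contain no telephone condition. Section 7.1 lets even the followed-up cases be contacted by telephone or by mail.

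**Hypothesis.** Section 3.4 will test whether "sarcoidosis patients will be more likely to be of low SES than controls". The other SES hypotheses in 3.4 compare cases with cases.

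**Geography.** Section 4.2.2 has the callers telephone households in the case's local community. Section 7.2 tells controls that they were found by "matching those of a particular patient with sarcoidosis within the same telephone exchange". Section 12.3.2.2 goes no further than "Random digit dialing may implicitly match cases and controls for geographical location".

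**The concern.** A case-control comparison needs controls drawn from the population that produced the cases. Here a person without a household telephone can become a case but can never become a control. For most exposures that may matter little. For SES it matters directly, because having a telephone is plausibly related to the exposure under test.

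Matching on age, gender and race does not remove the mismatch. Conditional logistic regression cannot adjust for it either, since SES is the exposure and not a confounder in this test. If people without telephones are poorer than average, the mechanism favours the study's own directional hypothesis, so part of a positive finding could come from the sampling frame.

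The protocol sets this standard itself. Section 1.3 lists possible bias in control selection among the main weaknesses of earlier studies, and section 2.3 faults one study for drawing a third of its controls from an urban clinic. It does not mention telephone coverage as a limitation.

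**Working it through.** **1. Reproduce the plan's power.** With one control per case, the formula in 12.2.1 reduces to power = Φ(δ√(N/ψ) − 1.96), where δ = p1 − p0. At correlation 0, ψ = p1 + p0 − 2·p1·p0.

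For N = 720, p0 = 0.30 and odds ratio (OR) 1.4:
- p1 = 0.42/1.12 = 0.375, δ = 0.075, ψ = 0.675 − 0.225 = 0.450.
- δ√(N/ψ) = 0.075 × 40 = 3.00, and Φ(1.04) = 0.851.

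The plan states 85.1% (12.2.1 and Table 2), so the formula can be reused.

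**2. Inputs for the bias.** From the protocol: 720 pairs and two-sided alpha 0.05, which is 2.5% in each direction. Assumed, because the protocol gives no coverage or SES figure:
- true OR of 1;
- low-SES share of 0.30 in telephone households;
- low-SES share s = 0.8 or 1.0 among cases without a telephone;
- share u of cases without a telephone, from 1% to 10%.

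**3. Formula.** Control share p0 = 0.30. Case share p1 = u·s + (1 − u)·0.30. Spurious OR = [p1/(1 − p1)] / [0.30/0.70].

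Example, u = 0.06 and s = 0.8: p1 = 0.048 + 0.282 = 0.330, so OR = 0.4925/0.4286 = 1.15. Then ψ = 0.432, δ√(N/ψ) = 0.03 × √(720/0.432) = 1.225, and Φ(1.225 − 1.96) = 23%.

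| u | s | p1 | Spurious OR | Significant in that direction (correlation 0) |
|---|---|---|---|---|
| 1% | 0.8 / 1.0 | 0.305 / 0.307 | 1.02 / 1.03 | 4.0% / 4.7% |
| 2% | 0.8 / 1.0 | 0.310 / 0.314 | 1.05 / 1.07 | 6.1% / 8.3% |
| 3% | 0.8 / 1.0 | 0.315 / 0.321 | 1.07 / 1.10 | 9.0% / 13.6% |
| 6% | 0.8 / 1.0 | 0.330 / 0.342 | 1.15 / 1.21 | 23.1% / 39.9% |
| 10% | 0.8 / 1.0 | 0.350 / 0.370 | 1.26 / 1.37 | 52.5% / 80.1% |

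The reference with no bias is 2.5%.

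**4. Two offsets, also assumed.**
- *Local calling.* Suppose cases without a telephone are 80% low SES and their controls, drawn from poorer areas, are 50%. At u = 10%, cases are 0.350 and controls 0.10 × 0.5 + 0.90 × 0.30 = 0.320, so OR = 1.14. At 3% and 6% it is 1.04 and 1.09.
- *Under-enrolment of poor cases.* Suppose 30% of the source population is of low SES, 5% has no telephone and 80% of that 5% is of low SES. Controls are (0.30 − 0.04)/0.95 = 0.274. If low-SES cases are 0.8 times as likely to be enrolled, cases are 0.24/(0.24 + 0.70) = 0.255, so OR = 0.91.

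**5. Power after restriction.** Losing 2%, 5% or 10% of pairs leaves 706, 684 or 648. For OR 1.4 at control exposure 0.30 and correlation 0, power is 84.4%, 83.2% or 81.2%.

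**The case against.** The strongest reply has four parts.

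**The frame is disclosed.** Section 6.3.1 says openly that households with telephones are sampled, and within that frame the word unbiased is fair. This stands, so the sentence is not false. Disclosure does not make the case group comparable, however, and the next claim, about a probability sample of the population, goes beyond the frame.

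**The direction is not established.** The protocol nowhere says that people without telephones are poorer. A reader might infer that the SES result must be biased towards low SES in cases. The documents do not support that. Local or same-exchange calling shrinks the effect, and under-enrolment of poor patients could reverse it. Section 2.2 reports an argument that some patients go unidentified in the health care system, and 6.2 requires the attending physician's permission before contact. This objection stands in full: only the direction of this one mechanism can be given, and only under the stated assumption.

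**Few such cases may enter the analysis.** Eligibility checks partly use telephone interviews (6.4). If the same-exchange description in 7.2 were applied literally, a case without a telephone might get no control and drop out of the matched analysis. This is possible, but 4.2.2 requires only calls to the case's local community, and no passage says such cases go unmatched. The protocol records nothing that would settle it.

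**The scope is narrow.** A reader might extend the problem to every case-control result, including HLA and immunogenetics. The documents do not support that either. Only one hypothesis in 3.4 sets cases against controls on SES, and for SES-linked exposures such as occupation, 12.3.2 plans adjustment for confounders.

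**Conclusion.** The concern holds in limited form. The protocol draws controls from telephone households and cases without that condition, then tests a directional SES difference between them. That is a mismatch of source populations which the planned analysis cannot correct for this hypothesis.

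Its size cannot be fixed from the document. Under the assumptions above it is minor if 1-2% of cases lack a telephone. From about 6% it is large enough to matter, with a false finding in the hypothesised direction about 23-40% of the time at 6% and 53-80% at 10%. The upper ends assume that every case without a telephone is of low SES, and none of these figures allows for local matching. The net bias remains unknown in both size and sign. Comparisons among cases only are unaffected.

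**What to change.** - At case registration, add one yes/no item: does the case live in a household with a telephone? For cases already enrolled, obtain it retrospectively where possible and report the unknowns. A contact number on file need not be a household line.
- In 12.3.2, base the primary case-control SES comparison on pairs whose case has a household telephone, with all pairs as a sensitivity analysis. For other SES-linked exposures, use the restriction only as a sensitivity analysis. Leave the genetic comparisons unrestricted.
- Report how many cases have no telephone and keep them in case-only analyses.
- In 6.3.1, and where the sentence recurs in 1.4, say that the controls approximate a probability sample of telephone households.

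The cost is one data item, a few sentences and a few percent of pairs in one comparison, with the small power loss shown in step 5. The primary SES result would then apply to telephone households. Even if few cases lack a telephone, the recorded count would show that the mismatch is unimportant, which the present plan cannot do.

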6.4 INCLUSION/EXCLUSION CRITERIA AND CONFIRMATION OF ELIGIBILITY

Only patients 18 years of age or older may be enrolled in the study. Patients cannot have active tuberculosis or be taking anti-tuberculosis therapy. Potential controls with a past history of sarcoidosis, chronic beryllium disease, fungal diseases treated with systemic chemotherapy, granulomatous hepatitis, primary biliary cirrhosis, Bell's palsy, uveitis, Crohn's disease, and erythema nodosum of unknown etiology are excluded from the study.

Potential cases and controls must be competent to sign consent forms for study participation and must be willing to participate for the length of the study. They may be excluded from the study if there is evidence that they may not comply with all study requirements. Potential cases and controls must be able to respond directly to questions on the study forms to be eligible for inclusion in the study. The eligibility of potential cases and controls is determined by the Clinical Center Coordinator through a combination of record review and telephone and personal interview. The Coordinator explains the nature of ACCESS to the potential cases and controls. If the potential case or control is interested in participating in ACCESS, the Coordinator administers a brief structured questionnaire addressing eligibility issues not gleaned from the medical record or telephone interview.

Potential cases and controls who are eligible and agree to enrollment, are asked to sign one or more consent forms to participate, depending upon the individual's case/control status (see Chapter 7). Cases and controls are identified only by a patient name code and identification number. The patient's name code and identification number serve to conceal the personal identity from the ACCESS Clinical Coordinating Center and Clinical Center staff and to maintain confidentiality. The patient's name code and identification number are recorded on separate ACCESS logs for cases and controls. These logs include the following information:

- 1. Date of initial contact.
- 2. Age.
- 3. Gender.
- 4. Race.
- 5. Health care coverage.

The reasons for ineligibility are recorded for all cases and controls deemed ineligible to participate in ACCESS. As noted in Section 6.2 completion of screening logs for cases was discontinued in October 1997.

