1.4 DESIGN FEATURES

Only newly diagnosed cases of sarcoidosis with tissue confirmation of granuloma and a clinical course compatible with sarcoidosis, that is, a systemic granulomatosis of unknown etiology are eligible for the study. Newly diagnosed cases are of interest for accuracy and consistency of recall. A newly diagnosed case is defined as a patient who had tissue confirmation less than six months prior to entry into the study. Initially, cases are recruited at each participating Clinical Center, without regard to type of clinical disease (i.e., erythema nodosum or Löfgren's Syndrome; acute or chronic sarcoidosis, excluding patients with fibrotic lung disease; fibrotic lung disease; or extrapulmonary sarcoidosis). Clinical Coordinating Center staff review the distribution of enrolled cases periodically to ensure that appropriate proportions of cases in each of the defined categories of disease are enrolled.

Population-based controls are selected through random digit dialing. Controls are matched to cases on age (within five years), gender and self-designated race (black, white, other). Random digit dialing facilitates the selection of a control group that approximates a probability sample in the population.

Only individuals 18 years of age or older are eligible. Cases or controls cannot have active tuberculosis or be taking anti-tuberculosis therapy or have a history of chronic beryllium disease. Potential controls with a past history of sarcoidosis, granulomatous hepatitis, primary biliary cirrhosis, Bell's palsy, undiagnosed uveitis, Crohn's disease and erythema nodosum of unknown etiology are excluded from the study. Cases and controls must be competent to sign consent forms for study participation and must be willing to participate in all required study evaluations.

Both cases and controls complete an entry evaluation for the collection of required data and biological specimens for future evaluation. The entry evaluation includes collection of demographic

information (age, gender, race, residence, marital status, etc.), medical history, environmental, and occupational exposure history, questions about the individual's family (first degree relatives), standardized psychosocial data on health related quality of life, and medical care usage.

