2. Sarcoidosis patients (cases) are more likely to report employment in particular occupations or occupational categories immediately prior to diagnosis of their sarcoidosis conditions when compared to non-sarcoidosis referent group (controls).

3. Sarcoidosis patients (cases) are more likely to have a "dose-related" risk associated with their employment in particular occupational/industrial categories when compared with non-sarcoidosis referent group (controls), based on duration of employment.

Determination of whether or not there is an increased frequency in cases as compared to controls of history of exposures to infectious agents is an important objective of ACCESS. Sarcoidosis may represent a granulomatous response initiated by an environmental, occupational and/or infectious agent.

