Multiorgan disease is defined as tissue confirmation in at least one organ, and either clinical or pathological involvement in another organ(s), as outlined in Table 6-1. The record of organ involvement for cases is based on abnormalities ever observed in the set of definitions in use November 1996 - March 1998, and in the revised definitions in use starting April 1998. The revisions made to the criteria for organ involvement in April 1998 were clarifications of wording, deletion of evidence of treatment response as a criterion (because almost none of the ACCESS cases have had a definitive course of treatment at the time of study entry and some of these abnormalities may respond to the same treatment if used for other diseases), and regrouping of the categories into those that are common, those that are unusual but serious, and other organ involvement.

Individuals with chronic beryllium disease are excluded from the study. Potential cases with occupational histories indicating possible beryllium exposure are excluded from the study unless both blood and bronchoalveolar lavage proliferation studies indicate a negative response to beryllium. Fungal lung disease and tuberculosis should be ruled out. Specifically, all cases should have acidfast bacillus (AFB) and fungal cultures of all available tissue performed and appropriately stained unless the diagnosis was confirmed by the Kveim agent. In potential cases undergoing bronchoscopy, bronchial washings should always be obtained specifically for fungal and AFB cultures. Potential cases who live in areas where histoplasmosis is endemic or who have risk factors for tuberculosis should have appropriate tests performed on tissue specimens (cultures of biopsy specimens required) to exclude tuberculosis and fungal infections (especially histoplasmosis). In particular, adequate samples should be cultured, if possible. At a minimum, slides of tissue should be stained for mycobacteria and fungi. Fungal serology and measures of H. capsulatum antigen are not expected to contribute to the diagnosis and are not used in ascertaining case eligibility. All slides for cases enrolled after September 1997 are reviewed under polarized light to determine whether birefringent material is present. A review for birefringent material on the slides of cases enrolled prior to September 1997 is performed if the slides are available.

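### A past history of systemically treated fungal disease bars controls but has no past-history counterpart for cases, so that history cannot be tested; the control exclusions in Sections 1.4 and 6.4 also disagree

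*Protocol*

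**What the plan says.** Section 6.4 lists who may not serve as a control: "Potential controls with a past history of sarcoidosis, chronic beryllium disease, fungal diseases treated with systemic chemotherapy, granulomatous hepatitis", followed by further conditions that include uveitis without qualification. The rule concerns past history and is written for controls only.

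For cases, Section 6.1 says "Fungal lung disease and tuberculosis should be ruled out". The means are laboratory ones: "fungal cultures of all available tissue performed and appropriately stained unless the diagnosis was confirmed by the Kveim agent". Nothing in Sections 1.4, 6.1 or 6.4 makes a past treated fungal infection a reason to exclude a case.

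Section 1.4 gives its own control list: "Potential controls with a past history of sarcoidosis, granulomatous hepatitis, primary biliary cirrhosis, Bell's palsy, undiagnosed uveitis, Crohn's disease", ending with erythema nodosum of unknown cause. Fungal disease is absent. The same section shows that the authors write a two-sided rule when they intend one: "Cases or controls cannot have active tuberculosis or be taking anti-tuberculosis therapy or have a history of chronic beryllium disease".

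Section 3.3 says that comparing cases and controls on "history of exposures to infectious agents is an important objective of ACCESS". Section 12.3.2.2 estimates the association for a categorical exposure from McNemar's test on matched pairs, with conditional logistic regression for adjusted analyses.

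**The concern.** In a matched case-control study, eligibility must not depend on an exposure differently in the two groups if that exposure is to be compared. A history of treated fungal disease is an infectious history, and infectious histories fall under the Section 3.3 objective. Screening it out of controls alone means every discordant pair on that factor must point towards cases, even if the factor has nothing to do with sarcoidosis.

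Two further things are at stake. Exposures that travel with fungal infection (Section 3.3 lists bird antigens, organic dusts, microbial bioaerosols and agricultural work) will be slightly under-represented in controls if they raise the risk of treated fungal disease. And because Sections 1.4 and 6.4 disagree, neither a recruiter nor an analyst can tell from the protocol alone which control definition was applied.

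**Working it through.** **Passages side by side**

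| Condition | Controls, 1.4 | Controls, 6.4 | Cases |
|---|---|---|---|
| Past systemically treated fungal disease | not listed | excluded | no past-history rule; fungal lung disease ruled out at diagnosis (6.1) |
| Uveitis | only if undiagnosed | any | not an exclusion |
| Chronic beryllium disease | excluded | excluded | excluded (1.4, 6.1) |

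**The plan's own figure.** The protocol gives no figure for this bias. The nearest is the matched-pair power in Section 12.2.1 and Table 2: odds ratio 2.0, 5% of controls exposed, correlation 0, 720 pairs, two-sided 0.05.

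- p1 = 2 × 0.05 / (1 + 0.05 × (2 − 1)) = 0.0952
- discordance ψ = p1 + p0 − 2·p1·p0 = 0.1357
- power = Φ(0.0452 × √(720/0.1357) − 1.96) = 0.909

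Table 2 prints 0.909. The figure reproduces, and the exclusion does not enter it.

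**Direct effect.** Let b be the number of pairs with only the case exposed and c the number with only the control exposed. The matched odds ratio is b/c. Eligibility under 6.4 sets c = 0. Hence b/0 is infinite if b ≥ 1, and 0/0 is undefined if b = 0.

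Assume no true association and a prevalence q of the history, equal in cases and in the source population. Then b ~ Binomial(720, q). With c = 0 the exact two-sided McNemar p-value is 2 × 0.5^b: 0.0625 at b = 5 and 0.031 at b = 6. The test is therefore significant when b ≥ 6.

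| Assumed q | Expected b = 720q | P(at least one such case) | P(false positive) |
|---|---|---|---|
| 0.1% | 0.72 | 0.51 | 0.0001 |
| 0.5% | 3.6 | 0.97 | 0.16 |
| 1% | 7.2 | 0.999 | 0.73 |
| 2% | 14.4 | 1.00 | 0.996 |

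**Spillover to a related exposure E.** Assume a true odds ratio of 1 for E. Let pE be the prevalence of E, and RR the risk ratio for treated fungal disease in people with E against those without.

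- q0 = q / (1 − pE + pE·RR) and qE = RR·q0
- removing the history from controls only gives a spurious odds ratio of (1 − q0)/(1 − qE)

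Example with q = 1%, RR = 10, pE = 5%: q0 = 0.01/1.45 = 0.0069, qE = 0.0690, spurious odds ratio = 0.9931/0.9310 = 1.067.

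Over RR of 2, 5 and 10 and pE of 5%, 10% and 30%, that is the largest value at q of 1% or less. The rejection rate stays between 5.0% and 5.9% against a nominal 5%. At q = 5% and pE = 10% the spurious odds ratio would be 1.05, 1.17 and 1.32 for RR of 2, 5 and 10. For an exposure inversely related to treated fungal disease, the bias runs downward.

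**With one rule for both groups.** The spurious odds ratio for E returns to 1.00. If neither group were screened, discordant pairs would balance in expectation, at about 7 each way for q = 1%.

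**The case against.** The strongest reply is that the exclusion has a sensible motive. Section 2.3 describes histoplasmosis as a common cause of disease resembling sarcoidosis, and Section 6.1 singles it out in the case work-up. Someone once treated for a fungal infection might have had unrecognised sarcoidosis, which is the same logic that supports excluding granulomatous hepatitis or Bell's palsy. That is plausible. But Section 6.4 does not give this reason, its wording covers any systemically treated fungal disease, and a good motive does not make the factor testable.

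It is also fair to say that cases are not unscreened for fungal disease. A reader might infer that they are, but Section 6.1 requires fungal lung disease to be ruled out and the tissue to show no other possible cause. The asymmetry covers only past or non-pulmonary treated disease, and these rules may remove some cases who carry the history, which would lower b.

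Third, treated fungal disease is not among the exposures that Section 3.3 enumerates. The objective refers only generally to infectious exposures, so no named analysis fails. This limits the consequence without removing it.

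Finally, a reader might want the criterion deleted from Section 6.4. Recruitment runs to June 1999 (Section 1.7) and the text already records a May 1998 change (Section 11.8), so deletion would create two control populations. An analysis restriction avoids that.

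**Conclusion.** The concern holds in a limited form. The one-sided past-history rule and the conflict between Sections 1.4 and 6.4 are both in the text and need no assumption. It also follows without assumption that past systemically treated fungal disease cannot be estimated as a risk factor in pairs enrolled under 6.4.

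The chance of a misleading significant result depends entirely on a prevalence that the documents do not give. It is negligible at 0.1% and near certain at 2%, and it further assumes that the diagnostic work-up removes no cases with the history.

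Two stronger readings are tempting and not supported. One is that the odds ratio is bound to be infinite: it is infinite only if at least one of the 720 cases has the history, a chance of about one half at 0.1%. The other is that the infectious and environmental findings as a whole are inflated. At 1% prevalence or less the spurious odds ratio does not pass about 1.07 on the grid examined, in a study sized for odds ratios near 2 at 5% exposure. A material distortion needs a prevalence of several percent together with a strong association. No stated power figure is affected.

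**What to change.** 1. Reconcile the control exclusion lists in Sections 1.4 and 6.4, for fungal disease and for uveitis, and record which version the telephone screener and Clinical Centers applied and when.
2. In the infectious and environmental analyses, apply the past-fungal rule to both groups by dropping pairs whose case reports such a history, as either the primary or a sensitivity analysis. First check that the medical history form captures it: Section 8.2 says medical history is collected from both groups, but the form is not in the document.
3. State that past systemically treated fungal disease will not be tested as a risk factor for pairs enrolled under the control-only rule.
4. Tabulate the potential controls turned away for this reason. Sections 6.3.1 and 6.4 already require reasons for ineligibility to be recorded, so this may give a rough idea of the unknown prevalence.

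The cost is a text correction, an analysis restriction and a small share of pairs in those analyses: about 7 of 720 if the history affects 1% of cases.
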